Economic Evaluation Supplement Aim: To understand the economic impact of the Southwest Hub interventions. We hypothesize that both the NH and ER interventions' reduction in participant suicidal ideation and improved resilience will reduce participant healthcare and other community and personal costs compared to the standard of care of CM alone.

1. Administer a time use survey (e.g. time-logs) and conduct in-person interviews among the project staff and health workers. Using these tools, we will ask staff to recall how they allocated their time and what resources (e.g. supplies, equipment, etc.) they used.
2. Analyze Celebrating Life Apache surveillance system (CL) data for related data points for study participants, including intake and follow-up case management visits. This data counts the number of times study staff visited or attempted to visit study participants, and is key in accounting for the time and financial costs of conducting study visits with participants.

Diversity Supplement Aim: To assess individual characteristics (age, gender, substance use history, mental health status, educational and employment status, family composition) associated with co-occurrence of suicide ideation or attempts and history of opioid use compared with suicide risks alone

Secondary Aims:

2. To examine mediators and moderators of treatment effectiveness and sequencing in order to determine which types and sequence of interventions is best suited for which youth.
3. To assess the acceptability, feasibility and capacity for sustainability of the Hub's key intervention components (Surveillance/Case Management, New Hope and Elders' Resilience) from the perspective of multiple stakeholders as they are implemented across different tribes. This will also include identifying, prioritizing and testing strategies aimed at enhancing the sustainability of tribally implemented suicide prevention programs.

Opioid Data Collection Sub-Study Aim: Explore community beliefs about: a) correlates of risk (i.e., other substance use, mental health status, family, demographic and social factors), b) protective factors (cultural and spiritual factors) and c) behavior functions (i.e., emotional regulation, reinforcement patterns) of opioid abuse in Native American youth through focus groups with the existing Community Advisory Boards from the Hub partners.

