Diversity Supplement Aim: To assess geospatial factors (neighborhood, and distances to opioid sources, treatment facilities or traditional care providers, school or workplace, or others in the sample with co-occurring disorders) associated with co-occurrence of suicide and opioid use.

II. Background and Rationale: Explain why this study is being done. Summarize briefly what is already known about the issue and reference previously published research, if relevant.

American Indian and Alaska Native (AIAN) youth bear a much greater burden of suicidal behavior compared to other U.S. youth.[1] **Mental health problems** such as depression, trauma, substance use (including opioids), impulsivity, self-injury, low self-esteem and hopelessness are key risk factors.[2] **Health system barriers**, including scarcity of mental health services and service providers, particularly Native ones, and lack of tribal-specific data for informing intervention development also negatively impact AIAN suicide rates.[3] However, unique AIAN cultural understanding of mental health, culturally-informed protective factors, and a preference for culturally-based healing modalities might not align with Western models of care.[4] A balanced **risk-reduction/resilience-focused and culturally-grounded approach** that addresses community risk factors and promotes protective factors holds promise for reducing suicide among AIAN youth.

The overall goal of the research component of the NIMH-funded Southwest Hub for American Indian Youth Suicide Prevention Research is to identify effective, feasible and sustainable interventions to prevent suicide and promote resilience among American Indian (AI) youth. The proposed study will **build on 20+ years of behavioral and mental health research and partnerships** undertaken by the Center for American Indian Health (CAIH) at Johns Hopkins with the White Mountain Apache Tribe (WMAT).

Our primary research aim, to be undertaken with the White Mountain Apache, includes: 1) **identification and voluntary enrollment of youth 10-29 years old using the WMAT established surveillance and case-management (CM) system** who recently had a validated suicide attempt, ideation, or binge substance use

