Aim 1: We will randomize **304 participants**; 76 to CM alone, 76 to CM+NH, 76 to CM+ ER, and 76 to CM+NH+ER. Based on the previous work with the SIQ, we believe a 25% reduction among individuals with a score of 30 or greater would represent clinically significant change in suicide ideation.[5] Using pilot data of NH among the WMAT, an average baseline score of 45 could be expected on the SIQ.[5] A clinically significant reduction translates into a large Cohen's D effect size (>0.8). However, we want the power to observe the more moderate effect expected to result from comparing the sequencing of the interventions (NH+ER vs. NH+CM vs. CM+ER vs. CM alone). Using an adjusted alpha to account for multiple comparisons of 0.013, and a correlation of 0.2 among repeated measures, with four groups (NH+ER vs. NH+CM vs. CM+ER vs. CM alone), $n=58$ people per group ($n=116$ randomized at each randomization time-point) would provide 80% power to detect a small to moderate effect (Cohen's $F=0.2$). Adjusting these estimates for 30% attrition would result in $n=76$ per each of the four groups ($n=152$ per arm) for a total sample size of $N=304$.

Please note for our ***the Opioid Data Collection Sub-Study***: We will use a mixed methods approach to examine opioid use among our SMART trial participants through addition of a quantitative opioid related measure and qualitative interviews ($N=30$) with a subset of those who endorse recent or current use.

For the economic evaluation supplement: We will use the same sample of participants as Aim 1. We are not drawing statistical inferences about cost estimates so there is no sample size requirement. Instead, we are reporting on the health care services utilization and costs incurred by study participants before, during and after the intervention. To administer a time use survey and conduct in-person interviews we will use all HUB program case managers (five or more) and healthcare providers (three or more).

For the diversity supplement: We will use a sub-sample of $n=239$ WMAT participants enrolled in the parent trial. This sample size is based on the estimated enrollment rates during the Diversity Supplement study period.

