Aim 3: Study participants will be 25-50 key stakeholders including youth, caregivers, program providers, community members, tribal leaders, and other researchers across the Hub, including satellite partners. Sample size for Aim 3 is based on qualitative research theory on saturation, a point after which common themes and information from respondents tend to converge. Quantitative data collected is exploratory in nature and will be used to help inform future implementation and scale-up of the programs.

Please note for our ***the Opioid Data Collection Sub-Study***: Key stakeholders will only be asked about opioid use generally in relation to the community, not their personal use. However, we are aware that personal use may still be disclosed. We will use the same referral and follow-up procedures for these participants as those in our SMART trial. We estimate 25 participants based on the number of Hubs sites and advisory board members.

IV. Participants:

Describe the study participants and the population from which they will be drawn. Specify the inclusion and exclusion criteria. If you plan to include children, note their ages and whether you will include children in foster care.

Note if the participants are particularly vulnerable in terms of cognitive limitations, education, legal migration status, incarceration, poverty, or some combination of factors.

Aim 1: Study participants will be self-identified Native Americans who are between the ages of 10 and 29 years old and reside on or near the Fort Apache Indian Reservation and are identified in the existing surveillance and case-management (CM) system as having recently had a validated suicide attempt, ideation, or binge substance use episode and recent ideation. The majority of these tribal populations lives below the federal poverty line. The economic evaluation supplement does not involve any contact with the study participants.

A. Inclusion Criteria:

- Native American youth ages 10 to 29 years old.
- Reside on or near the Fort Apache Indian Reservation.
- Parent/guardian consent for youth under 18 years old.
- Suicide ideation, binge substance use with recent (i.e. within the last 3 months) suicide ideation, or suicide attempt in the past 30 days as identified and verified by the surveillance system OR release from inpatient care related to suicide ideation or attempt within past 30 days

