For the diversity supplement: We will capture an ID (from registry) in the Celebrating Life Surveillance System to link them to Hub (parent grant) data and the location of the index event (from registry) that triggered their involvement with the Hub study. We will use GIS (ArcGIS Pro 2.4, ESRI, Redlands, CA) to map GPS locations of each event and all participants' home locations to determine places of opioid co-occurring and non-opioid cooccurring suicidal individuals. Following this, we will perform a global test for hotspots of all types of suicidal behavior and opioid use across the entire community through the use of a population-based spatial cluster analysis. United States Census data will be utilized to determine the underlying population of the community surrounding each suicidal event and reported opioid location. The expected incidence of co-occurrence of suicidal and opioid behavior will be calculated by assuming a uniform event per population distribution throughout the community. Next, spatial Statistics will identify a critical distance at which the clustering occurs in the dataset and then test for local clustering. Hotspot maps will be created to identify social patterns of suicide and opioid use that are informative for approachable visualization and interpretation by community members to generate insights and community-based participatory research (CBPR) approaches to future intervention. After visual maps are produced and clustering is determined, the information will be quantified and used for regression models. These regression models that account for geospatial data explicitly adjust for possible dependency structures that may be present.

Additional Measures:

Aims 1 & 2:

Centers for Epidemiologic Studies of Depression – Revised 10-item version (CESDR-10) is a self-report scale used to measure depressive symptoms (Cronbach's alpha ranged from 0.90 to 0.91 in a validation study) [35]. The full version has been widely used among adolescent and AI populations, including Apache youth.[5, 30, 31]

Children's Negative Cognitive Errors Scale is a 17-item self-report scale that assesses cognitions about social/peer rejection, group activity competence and academic competence, and demonstrated excellent internal consistency reliability (Cronbach's alpha=0.89). It has been previously used in a sample of Apache youth.[5, 32]

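### The population-based hotspot null cannot separate clustering of opioid co-occurrence from area differences in age structure, suicide-event rate, and surveillance capture or enrolment

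*Combined protocol and SAP*

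**What the plan says.** The supplement has two aims in Section I. The individual-level aim looks for characteristics "associated with co-occurrence of suicide ideation or attempts and history of opioid use compared with suicide risks alone". The geospatial aim looks for spatial factors "associated with co-occurrence of suicide and opioid use" and names no comparator.

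Section V.C.4, Aim 2, gives the spatial method. Event and home locations are mapped for participants with and without opioid co-occurrence. A population-based cluster analysis then tests for hotspots of suicidal behaviour and opioid use over the whole community. Census data supply the underlying population, and expected co-occurrence is obtained by "assuming a uniform event per population distribution throughout the community". Local clustering is tested next, hotspot maps are drawn for community use, and the results are quantified for regression models that allow for spatial dependence.

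The cases are described elsewhere. Section III.B says the supplement uses a "sub-sample of $n=239$ WMAT participants enrolled in the parent trial" and adds: "This sample size is based on the estimated enrollment rates during the Diversity Supplement study period". Section IV.A limits participants to "Native American youth ages 10 to 29 years old" who live on or near the reservation and have a qualifying event: "Suicide ideation, binge substance use with recent (i.e. within the last 3 months) suicide ideation, or suicide attempt in the past 30 days" (or a recent related inpatient discharge). Section II describes "identification and voluntary enrollment of youth 10-29 years old using the WMAT established surveillance" and case-management system. Section III.A adds the opioid location questions to the trial survey. No section says that Census counts will be limited by age, or that differences in capture or enrolment between areas will be adjusted for.

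**The concern.** The numerator and the denominator describe different populations. The expected count depends only on how many people live in an area. The observed count also depends on how many of them are aged 10-29, how often they have a suicide-related event, whether surveillance records it, whether they agree to enrol, and only then on whether they use opioids. A rejection of the uniform null says that at least one of these factors varies by place; it does not say which.

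The maps are meant to be read by community members and to inform later place-based work, and the cluster results go on into regressions. If an area is marked as a co-occurrence hotspot because it is younger or was recruited more fully, both uses inherit the error. The opposite also matters: an area with heavy opioid co-occurrence but poor recruitment can look unremarkable. Allowing for spatial dependence in the regressions does not repair a mismatched reference population.

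**Working it through.** **Inputs from the documents.** Sample 239 (Section III.B), which is 239/304 = 78.6% of the planned trial. Age 10-29 and a qualifying event (Section IV.A). Voluntary enrolment through surveillance (Section II). Uniform events per head as the null (Section V.C.4). The documents give no opioid share, number of areas, area populations, alpha or power for the spatial test, and no formula behind 239, so there is no planned figure to reproduce.

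**Structure.** For area *i*, let P = Census population, a = share eligible by age, s = suicide-event rate, e = capture and enrolment, q = opioid share among participants, and C = total co-occurring cases.

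- Expected under the plan: C × P_i / ΣP.
- Mean observed: P_i × a_i × s_i × e_i × q_i.
- Observed/expected is therefore proportional to a_i × s_i × e_i × q_i.

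If the target is the opioid share among suicidal youth, it is q_i, and a, s and e are nuisances. If the target is joint burden per eligible person, it is s_i × q_i, and a and e remain nuisances. In a within-sample comparison the proportion co-occurring in area *i* is q_i; a, s and e cancel, provided enrolment does not differ by opioid use in a way that varies by area.

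**Hand illustration (assumed: 20% co-occurring everywhere, two areas of equal population).** Cases = 239 × 0.20 = 47.8; expected 23.9 per area. Chi-square (1 df) = 2 × (observed − 23.9)² / 23.9.

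| Participants from area 1 | Ratio of areas | Cases, areas 1 / 2 | Chi-square | p |
|---|---|---|---|---|
| 60% | 1.5 | 28.7 / 19.1 | 1.91 | 0.17 |
| 70% | 2.3 | 33.5 / 14.3 | 7.65 | 0.006 |
| 75% | 3.0 | 35.9 / 12.0 | 11.95 | 0.0005 |

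The opioid share is identical in both areas in every row.

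**Simulation (assumed: six areas of equal population, 239 participants, nominal 5% level, 20,000 runs per scenario).** The ratio is one area's combined age-structure, suicide-event and enrolment rate relative to the others. The planned null is a chi-square of co-occurring cases against population; the within-sample test is a chi-square of co-occurring against non-co-occurring participants by area. Ranges run over overall opioid shares of 10%, 20% and 30%.

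| Scenario | Planned null rejects | Within-sample test rejects |
|---|---|---|
| Opioid share equal, ratio 1 | 4-5% | 5% |
| Opioid share equal, ratio 1.5 | 8-16% | 5% |
| Opioid share equal, ratio 2 | 18-48% | 5% |
| Opioid share equal, ratio 3 | 46-93% | 5% |
| Opioid share doubled in one area, ratio 1 | 21-55% | 23-80% |
| Opioid share doubled in one area, ratio 0.5 | 4-5% | 18-56% |

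Rows two to four show rejection with no difference in opioid share. The last row shows masking: a doubled share disappears when that area's contribution is halved. The fifth row shows that the planned null does respond to opioid clustering when nothing else varies.

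**The case against.** A reader might infer that the map shows enrolment and suicide risk and not opioid co-occurrence at all. That goes too far. The counts carry the opioid share along with the other factors, and under uniform enrolment the planned test picks up a doubled share.

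A reader might also infer that the supplement has already fixed suicide-alone as the spatial comparator. The documents do not support this. That contrast is stated for individual characteristics; the geospatial aim names no comparator, and Section III.A speaks of the clustering of both suicide risk and opioid use. If joint burden per head is the target, a higher local suicide-event rate is signal, and a population denominator is a sensible starting point. That part of the objection stands. It does not rescue the denominator, because age structure and enrolment are nuisances on either reading.

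Nor do the documents state an all-ages denominator. It is the natural reading, but the analysis section is brief and simply silent on age. Likewise nothing says that enrolment varies by area: surveillance staff try to see everyone reported for self-injury, and recruitment takes place at home or in another private place, which limits distance as a cause. The illustrations therefore show what could happen, not what will, and simple area chi-squares are not the planned cluster analysis.

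Finally, the plan does map the non-co-occurring participants, and it leaves the outcome of the spatial regressions unstated, so those regressions cannot be assumed to inherit the population null. But the comparison group is not used in the expected count, which is where it is needed.

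**Conclusion.** The point holds in this form: as written, the population-based null cannot tell clustering of opioid co-occurrence from area differences in the share aged 10-29, suicide-event rate, and surveillance capture or enrolment. The mismatch is in the current text and no other section corrects it.

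Its size is unknown, because the documents give no area-level figures. On the assumed inputs, a 1.5-fold difference between areas raises the rejection rate modestly (8-16%), while a threefold difference can make rejection likely (46-93%) with no difference in opioid share. The direction follows from the structure and does not depend on those inputs.

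This is a supplement analysis that does not touch the trial's primary outcome, so the point is a cheap improvement. It is not grounds for discarding the per-population analysis: replacing that outright would change the question.

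**What to change.** In Section V.C.4, Aim 2 (diversity supplement):

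- Add a case-control (Bernoulli) spatial scan, with co-occurring participants as cases and the already mapped non-co-occurring participants as controls, permuting the labels over the fixed locations.
- Base any claim about clustering of opioid co-occurrence among suicidal youth on that scan, including any cluster terms carried into the regressions.
- Keep the population-based map as a secondary description. Use Census counts for the eligible population aged 10-29 (Native American where available), and label it as enrolled events, not community incidence.

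The cost is analysis wording and one more analysis; the locations are already to be collected. The main downside is small numbers. At an assumed co-occurring share of 20% there would be about 48 cases and 191 controls (239 × 0.20 = 47.8; 239 − 47.8 = 191.2); at 10%, about 24 and 215; at 30%, about 72 and 167. Small clusters will be hard to find: at the 10% share, the simulated within-sample test detected a doubled share in one of six areas in only 23% of runs.

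The scan removes enrolment bias only if area differences in enrolment do not depend on opioid use. Section IV.B excludes people whose drug use problem needs inpatient treatment, so this condition should be stated as an assumption when the results are reported.

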Due to anticipated sample sizes, proposed mediation and moderation models are hypothesis generating. Potential moderators such as gender or age will be evaluated by including them at the appropriate level of measurement in the models detailed in Section C (page 10) and interactions terms will be specified between moderator and intervention terms of interest.

For the diversity supplement, we will use spatial data collected as part of the parent grant data collection, including home addresses and GPS stamp, and information about the specific location where the index event took place using geographic code to pin major locations across the reservation. We will capture an ID (from registry) from the Celebrating Life Surveillance System to link participants to parent grant data and the location of the index event (from registry) that triggered their involvement with the parent grant study. In addition to data that is currently being collected, we will work with study team members, community stakeholders via parent grant community advisory board (CAB) to identify and add geographic data points of potential interest—such as health facilities, treatment centers, schools, police stations, and community gathering locations to help understand the interplay of geography and spatial clustering of suicide risk and opioid use to inform future place-based intervention design.

United States Census data will be merged in our data sets to identify tracts in which individuals live to inform the spatial statistical models. Two additional geographical questions will also be added to the parent grant survey for all assessment periods to assure that we are capturing relevant information for those that indicate recent opioid use: 1) where do individuals acquire opioids?, and 2) where do individuals use opioids?

Aim 3. To assess the acceptability, feasibility and capacity for sustainability of the Hub's key intervention components (New Hope, Elders Resilience Curriculum, and CM) from the perspective of multiple stakeholders as they are implemented across different tribes.

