For the diversity supplement: Data will be analyzed in several stages to assess the association of individual characteristics and the co-occurrence of suicide ideation or attempts and opioid use compared to individuals with suicide ideation or attempts alone. First, data will be explored to understand the univariate distributions for this population. Second, bivariate associations will be explored between those with co-occurrence compared to those with suicide risk alone. We will use chi-square tests to test the association of all dichotomous independent variables against the outcome variable (suicide behavior and opioid co-occurrence vs suicide behavior alone). For continuous independent variables, simple generalized linear models will be fitted with one independent variable while specifying a binomial family distribution with a logit link function. After a foundational understanding of the bivariate relationships is established, we will use generalized linear regression models to investigate the multivariate relationships between individual characteristics on the outcome of either co-morbid suicidal behaviors and opioid use (1) vs. suicidal behaviors alone (0). All models will control for gender and age. All analyses will be conducted in the current version of R using a variety of packages necessary.

Aim 2: Potential moderators such as gender or age will be evaluated by including them at the appropriate level of measurement in the models detailed above, and interactions terms will be specified between moderator and intervention terms of interest. Key mediators include connectedness, self- esteem and cultural identity. Hypothesized moderators for both interventions include: gender, age and event type. We will also examine adolescent depression, negative cognitive thinking, and family functioning.

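### The diversity supplement's spatial analysis lists a predictor of suicide-opioid co-occurrence that is computed from that outcome, and leaves room for others, so ordinary p-values for these predictors cannot be trusted

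*Combined protocol and SAP*

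**What the plan says.** Section I states the spatial aim of the diversity supplement: to assess neighbourhood and "distances to opioid sources, treatment facilities or traditional care providers, school or workplace, or others in the sample with co-occurring disorders" as factors "associated with co-occurrence of suicide and opioid use". The data analysis plan (Section V.C.4) codes the supplement's outcome as 1 for suicidal behaviour with opioid use and 0 for suicidal behaviour alone. It does so for the individual-characteristics models and names no separate outcome for the spatial models.

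Section III.A (Aim 2) gives two kinds of location. Two new survey items are meant "for those that indicate recent opioid use: 1) where do individuals acquire opioids?, and 2) where do individuals use opioids". Other points are to be added with community input, "such as health facilities, treatment centers, schools, police stations, and community gathering locations".

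For Aim 2, Section V.C.4 maps participants by co-occurrence status, runs a global hotspot test covering all suicidal behaviour and opioid use, and calculates expected co-occurrence from Census population. Then "spatial Statistics will identify a critical distance at which the clustering occurs in the dataset and then test for local clustering". After that, "After visual maps are produced and clustering is determined, the information will be quantified and used for regression models". The one safeguard given is that the regressions adjust for possible dependency structures. The plan describes no permutation reference, hold-out sample or leave-one-out rule. Section III.B sets the sample at 239 from expected enrolment, with no alpha or power.

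**The concern.** A regression test is valid when the predictor's values can be treated as fixed and do not depend on the outcomes being modelled. Distance to other co-occurring participants breaks that condition, because changing who is co-occurring changes the predictor. A co-occurrence hotspot breaks it more severely, because the participant's own status usually helps to create the hotspot. Choosing the clustering distance where clustering looks strongest, then testing at that distance on the same data, adds a selection effect.

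Section III.A says this work is to inform place-based interventions, and Section V.C.4 says the maps go to community members. A false hotspot could misdirect effort or label a neighbourhood.

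**Working it through.** **No figure to reproduce.** The plan gives no error rate or power for the spatial models. The check is therefore whether each kind of predictor keeps its nominal level when co-occurrence is unrelated to place. The 5% level, prevalence, home layout, cluster statistic and hotspot cut-off are all assumptions.

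**Which listed factors depend on the outcome**

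| Factor | Built from co-occurrence status? |
|---|---|
| Distance to other co-occurring participants | Yes, by definition |
| Distance to opioid sources | Yes, if sources come from the items for recent users |
| Co-occurrence hotspot or cluster membership | Yes, if used as a predictor (role not stated) |
| Neighbourhood; distance to facilities, providers, school or workplace | No |
| Hotspot of all suicidal events, ignoring opioid use | No; everyone in the sample is suicidal |

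**Why a hotspot flag is circular.** Take the local Gi* statistic, with y as co-occurrence status and w the number of participants within the radius, including oneself:

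Gi* = (cases within radius − ȳw) / (S·√[(nw − w²)/(n − 1)])

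With n = 239 and 20% prevalence there are 48 cases, so ȳ = 48/239 = 0.201 and S = √(0.201 × 0.799) = 0.401. A radius at the 5th percentile of pairwise distances gives w ≈ 0.05 × 238 + 1 = 12.9, say 13. The denominator is 0.401 × √[(239 × 13 − 169)/238] = 0.401 × 3.513 = 1.408. A flag at Gi* > 1.96 needs more than 0.201 × 13 + 1.96 × 1.408 = 5.37 cases, that is, at least 6 of 13.

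A co-occurring youth supplies one of the six and needs 5 of the 12 neighbours. Any other youth needs 6 of 12. Under random labels the hypergeometric probabilities are 6.4% (12 drawn from 238 containing 47 cases) and 1.7% (12 drawn from 238 containing 48). Co-occurring youth are thus 0.0642/0.0174 = 3.7 times as likely to be flagged, with no spatial effect at all.

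**Simulated false-positive rates.** Setup: 239 participants, labels assigned at random, one logistic regression per variable, likelihood-ratio test at 5%, 1,000 datasets per scenario, no covariates. The Monte Carlo standard error at 5% is √(0.05 × 0.95/1000) = 0.7 points.

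| Predictor | 10%, uniform | 10%, clustered | 20%, uniform | 20%, clustered | 30%, uniform | 30%, clustered |
|---|---|---|---|---|---|---|
| Distance to nearest *other* co-occurring youth | 19.8% | 23.7% | 17.9% | 12.2% | 15.1% | 10.5% |
| Gi* flag > 1.96 | 45.1% | 56.2% | 45.1% | 65.4% | 45.0% | 53.0% |
| Distance to nearest source reported by *others* | 18.6% | 17.4% | 12.2% | 10.2% | 9.7% | 6.9% |
| Distance to fixed facility | 5.3% | 4.6% | 3.8% | 7.1% | 5.8% | 5.9% |
| Density of all suicidal participants | 7.6% | 6.2% | 5.4% | 4.8% | 5.3% | 6.1% |

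The source row assumes that reported sources lie near the reporter's home. If a youth's own reported source is included, the rate is 29-100%.

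Two other setups agree:
- Nine settlements, 30/45/70 cases, age and gender adjusted, 1,500 datasets each: 77%/76%/73% for the hotspot flag and 14%/11%/11% for distance to the nearest other case.
- Uniform or clustered homes, 30/45/70 cases: 46-59% for the flag, 12-20% for distance to the nearest other case, and 3-6% for a fixed facility.

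**Data-chosen distance.** In the nine-settlement setup, a one-sided 5% overall clustering test at the peak distance rejected in 26%/26%/22% of datasets. This is one overall test; error in the plan's local tests was not simulated.

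**Does dependence adjustment help?** With nine settlements, 30/45/70 cases and 400 datasets each, the flag was significant in 72%/67%/67% with age and gender only, 56%/57%/56% with a quadratic spatial surface, and 52%/53%/50% with settlement fixed effects. Distance to the nearest other case rose from 15%/16%/11% to 37%/26%/16% with settlement effects. These are two simple adjustments, and some fits gave convergence warnings.

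**The case against.** A reader might infer that the plan enters hotspot membership as a predictor of co-occurrence, that all its spatial distances are circular, and that a false association is therefore certain. The documents do not support this.

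The role of the cluster information is not stated. It could mean mapped distances to facilities, or the critical distance used to set up the dependence structure. Most listed distances do not depend on the outcome, and the global hotspot test is not confined to co-occurrence. The highest rates belong to the inferred predictor under an assumed statistic. For the one outcome-derived factor that is named outright, the rate is about 11-24%: inflated, but far from certain. The simulations also apply local statistics to enrolled youth, whereas the plan describes a population-based analysis with Census expected counts. Models that include neighbours' outcomes as the dependence term are legitimate, so adjustment is not useless in principle. Finally, this is an exploratory supplement aim.

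All of that stands, and it narrows the point. It does not remove the named outcome-derived factor, the reuse of the same data to choose the distance and test for clustering, or the absence of a reference distribution that allows for either.

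**Conclusion.** The concern holds in limited form. Distance to other co-occurring participants is a stated predictor computed from the outcome. Participant-reported opioid sources would be another. Co-occurrence hotspot membership would be the most serious, if it is used as a predictor. With no true effect and a nominal 5%, illustrative rates are about 11-24% for neighbour distance and about 45-77% for a Gi* hotspot flag, against about 3-7% for fixed facilities. The exact rates rest on assumed layouts, prevalences and cluster statistics; the dependence on the outcome does not. Adjusting for residual spatial dependence does not by itself remove the problem. Neighbourhood, distances to facilities, providers, school or workplace, and hotspots of all suicidal events are unaffected. Severity is moderate: the inference of one supplement aim is at risk, and the SMART primary analysis is not.

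**What to change.** State how each spatial covariate is built and what role the cluster results play in the regressions. Then:

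1. Keep co-occurrence hotspot or cluster membership descriptive. Do not enter it as a predictor of co-occurrence.
2. Test clustering, and any distance to other co-occurring participants, against random relabelling of co-occurrence status among enrolled youth. Recompute the whole procedure for each relabelling and report one p-value for the maximum over all distances examined. Neighbour distance need not be banned; it needs this reference. Omitting only the participant's own record is not enough, as the 11-24% shows.
3. Limit ordinary regression inference to locations fixed independently of the outcome, with a term for residual spatial dependence. Opioid sources qualify only if identified independently of participants' answers; otherwise report those distances descriptively.

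The cost is analysis-plan wording, a permutation run on data already being collected, and fewer nominally significant spatial predictors. No new data are needed.
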